Specific Aim 3. To determine whether growth hormone therapy-induced changes in fatigue and cognition correlate to changes in the GI microbiome. - mTBI/PASC Baseline (month 0) vs. mTBI/PASC Month 6 – Changes in GI microbiome of mTBI or PASC patients will be correlated to fatigue/cognition symptom resolution in response to growth hormone treatment. Healthy

controls will provide control data. Controls will not receive rhGH treatment. **Outcomes:** Changes in genus, species, Questionnaires (GSRS (GI), MoCA (cognition), BFI and MFSI (fatigue)).

Secondary Aims and Symptom-Related Outcomes and Assessment of Body Composition and Metabolism:

Specific Aim 4a. To determine whether growth hormone therapy alters mood, sleep quality, and quality of life. Mood, sleep, and quality of life will be measured at baseline (month 0) and month 6. (POMS (mood/QOL), QOL-AGHDA (QOL of growth hormone (GH) deficiency), PSQI (sleep), FPQ (food preferences)).

4b. To determine whether growth hormone therapy alters body composition and muscle function. Skeletal muscle mass, as derived from lean body mass determinations, and fat mass will be measured using dual energy x-ray absorptiometry (DEXA) at baseline (month 0) and month 6. (DEXA, Biodex, 6 min walk).

4c. To determine whether growth hormone therapy alters resting energy expenditure. Resting energy expenditure (REE) will be measured using indirect calorimetry at baseline (month 0) and month 6.

Background and Significance

Annually 1.5 million children and adults experience trauma to the head and brain that results in a traumatic brain injury (TBI). While TBI are classified as severe, moderate, or mild based upon the Glasgow Coma Scale (GCS), of the more than 1.5 million people who experience a TBI each year, as many as 90% sustain a mild TBI (mTBI) (1). mTBI can occur during organized sport (football, soccer), home recreation (bike riding, skateboarding), and as a result of a motor vehicle accident or other physical traumatic event. The term 'mild TBI' is misleading as we now know that a significant proportion of mTBI patients suffer from significant impairments or disabilities for many years following the initial brain injury. These include, "foggy brain," short-term memory loss, (1) impaired conversational abilities, and inability to organize daily activities. Together, this symptom complex renders many individuals unable to function in school or maintain a job.

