Notably, the cluster of symptoms associated with post-COVID syndrome include profound fatigue and cognitive dysfunction, which are strikingly consistent with BIAFAC. While studies are underway to understand the details of the mechanism causing BIAFAC and why GH treatment alleviates symptoms in these patients, we are intrigued that the symptom phenotype with post-COVID patients overlaps with many BIAFAC symptoms. It is possible that post-COVID syndrome may be addressed through similar treatment strategies including the potential for prebiotic/probiotic enhancement of microbiome health.

Therefore, in the current study we will assess the GI microbiota in individuals with a history of mTBI or PASC and fatigue. Each participant's baseline will serve as an individual control. An additional and critical control dataset that will be used for comparisons will be provided by analysis of the GI microbiome from healthy controls. Furthermore, we will investigate whether treatment with recombinant Human Growth Hormone (rhGH) will create changes in the gut flora producing microbiomes more similar to those expected in healthy controls and whether these changes correlate with the expected improvements in fatigue, cognition, brain activation, and brain morphology in the mTBI or PASC patients.

Experimental Design and Methods

Enrollment

TBI subjects: To address **AIM 1a** and **AIM 1b** we will study subjects with a history of mild TBI enrolled into either **arm 1** (n=25) or **arm 2** (n=25) for a total of (**n=50**).

Healthy Controls: To address **AIM 1** and **AIM 3** we will study healthy control subjects enrolled into either **arm 1** (n=25) or **arm 2** (n=25) for a total of (**n=50**).

[figure not shown]
PASC subjects: To address **AIM 3** we will study subjects with a history of COVID-19 and PASC symptoms enrolled into **arm 3** (**n=25**).

ARM 1: mTBI and Household Controls

Subjects. We will study subjects (aged 18-70 years) with a history of mild TBI (n=25) and their household controls (aged 18 years and up) (n=25). mTBI subjects will undergo a 6-month intervention of rhGH therapy (See Figure 1). Household controls will be asked to participate in questionnaires, blood draws (amino acid analysis), and fecal sampling (GI microbiome analysis). Household controls will not receive any growth hormone treatment.

mTBI group

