- Gastrointestinal Symptom questionnaire. Gastrointestinal symptoms will be monitored monthly using the Gastrointestinal Symptom Rating Scale (GSRS). The GSRS is a 15-item questionnaire. Each question has a seven-point Likert-type scale where 1 represents absence of symptoms and 7 represents very troublesome symptoms. The GSRS will be measured monthly.

For Arm 1 only: If the mTBI subject sustains an additional TBI during the study period, the study will be extended for both the mTBI and household control for an additional 6 months. The GSRS will be collected monthly during the 6 month extension.

○

Statistical Considerations

Aim 1a:

In this protocol we intend to compare the GI microbiome of diagnosed mTBI patients against the microbiome of healthy controls (HC). Data will be organized by time (PRE vs. POST) and by treatment (mTBI vs. HC). The hypothesis is that group differences between mTBI and HC will exist at PRE but that GH treatment in the mTBI group will dissolve these differences at POST.

Power calculations using q-PCR data from 22 diagnosed TBI patients and 15 healthy control subjects suggesting that we will be able to detect group differences in genus and/or species in the intestinal flora. These calculations suggest that we would need about 6 subjects per group to have an 80% probability of detecting significant differences in at least one of the previously

identified organisms (two-sided, $\alpha=0.05$). With the proposed subject numbers (25 per group) we calculate that the power would be between 91 – 100 % for at least 8 of the previously identified organisms.

Aim 1b:

Given our recent results from mTBI patients with BIAFAC, that identified two distinct community groups, based upon the presence of specific *Prevotella* species, we require additional participants to achieve group sizes of each type to address differences in the individual species for the pre and post comparisons. Enrollment: We expect to enroll subjects without the need for a HHC to address these differences. These subjects will be compared to matched normal participants from the general population adding 25 TBI and 25 normals to the study creating the power needed to address *Prevotella* positive and negative community types.

[figure not shown]
Aim 2:

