Odoribacter	52.5%	71.5%	83.8%	91.2%
Ruminococcus bicirculans	57.2%	76.3%	87.7%	93.9%
Bacteroides vulgatus	65.6%	83.9%	93.1%	97.2%
Sutterella	53.0%	72.0%	84.2%	91.5%
Lachnoclostridium	30.8%	44.4%	56.4%	66.4%
Streptococcus salivarius	27.8%	40.2%	51.4%	61.2%
16s	6.8%	7.8%	8.8%	9.8%

Study Timeline

Interventional, mechanistic studies such as this one are routinely performed by our research group and involve fine coordination between our team and the Clinical Research Center at UTMB. From experience, we know that we will be able to complete ~16 experiments of this type of trial per year. Thus, we anticipate completing all patients at the end of year 3. Therefore, a 3-year span is needed to accomplish all aims, and data analysis and manuscript writing will follow.

Protection of Human Subjects

A. Risks to Human Subjects

Human subject involvement and characteristics. Arm 1: We propose to study a total of 50 patients both males and females, with a history of mild TBI (n=25) ages 18 to 70 and their household controls (n=25) ages 18 and up. As the mTBI subjects will be selected for study based on their history and symptom complex, we expect that screening failures will be low (approximately 20). We also expect approximately 4 sets (8 total) of subjects to drop out during the course of the study. Thus, in order to achieve a total of 25 pairs (50 individuals) completing the study, we anticipate screening and enrolling approximately 78, but up to 100 individuals over 3 years. Arm 2: We propose to study a total of 50 patients both male and female consisting of patients with a history of mild TBI (n=25) and healthy matched controls (n=25), ages 18-70. As the mTBI subjects will be selected for study based on their history and symptom complex, we expect that screening failures will be low. Arm

3: We propose to study a total of 25 patients both male and female consisting of patients with a history of COVID-19 ages 18 – 70. As PASC subjects will be selected for the study based on their history and symptom complex, we expect that screening failures will be low.

ARM 1:

1. mTBI Inclusion criteria Male or female with a diagnosis of mild TBI.
2. At least 6-month post-injury.
3. Ages 18 to 70 years.
4. Lives in same household as paired control that meets inclusion/exclusion criteria.
5. Participant is willing and able to give informed consent for participation in the study.

mTBI Exclusion criteria

1. Unable to walk unassisted.

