2. Significant heart, liver, kidney, blood or respiratory disease.
3. History of chest pain or coronary heart disease.
4. Uncontrolled Diabetes mellitus.
5. Any history of a recently (12 months) diagnosed cancer other than a skin cancer (excluding melanoma).
6. Current alcohol or drug abuse.
7. Premorbid history of psychiatric disorder.
8. Premorbid history of head trauma.
9. Pregnancy or become pregnant during the trial.
10. Subjects who are deficient in cortisol or thyroid at screening will be excluded until hormone abnormalities have been corrected.
11. Subjects with chronic pain who are being managed with narcotics will be excluded as the effects of central nervous system depressants may interfere with study test results.
12. Subjects with a history of inflammatory bowel disease, Celiac disease or active diverticular disease.
13. Subjects with MRI incompatible devices.
14. Subjects with severe claustrophobia.
15. Other medical condition or medication administration deemed exclusionary by the study investigators.

Household Control Inclusion criteria

1. Ages 18 and up.
2. Lives in same household as paired mTBI subject that meets inclusion/exclusion criteria.
3. Participant is willing and able to give informed consent for participation in the study.

Household Control Exclusion criteria

1. Significant heart, liver, kidney, blood or respiratory disease.
2. Uncontrolled Diabetes mellitus.
3. Any history of a recently (12 months) diagnosed cancer other than a skin cancer (excluding melanoma).
4. Current alcohol or drug abuse.
5. Premorbid history of psychiatric disorder.
6. Premorbid history of head trauma.

7. Pregnancy or become pregnant during the trial.
8. Subjects who are deficient in thyroid at screening will be excluded until thyroid hormone is replaced.
9. Subjects with a history of inflammatory bowel disease, Celiac disease or active diverticular disease.
10. Other medical condition or medication administration deemed exclusionary by the study investigators.

ARM 2:

mTBI Inclusion criteria

1. Male or female with a diagnosis of mild TBI.
2. At least 6-month post-injury.
3. Ages 18 to 70 years.
4. Participant is willing and able to give informed consent for participation in the study.

mTBI Exclusion criteria

1. Unable to walk unassisted.
2. Significant heart, liver, kidney, blood or respiratory disease.
3. History of chest pain or coronary heart disease.
4. Uncontrolled Diabetes mellitus.

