- d. To minimize the possibility of coercion or undue influence all subjects will be given a copy of the approved consent forms and encouraged to discuss with their families prior to meeting the coordinator for the consenting process. The study team will be make it very clear to the potential mTBI participants that to meet inclusion criteria for this study, they must have an eligible household partner. If either one of the pair withdraws consent or is terminated, the other will be terminated by the study team.
- e. We are requesting an alteration of the consenting process so that we can obtain written consent and perform the medical screening in the same visit. The medical screening requires an overnight fast, which the IRB deems as research. Subjects will be provided a copy of the approved consent form for their review prior to their consenting/screening visit. The risk involved is an overnight fast. An overnight fast for medical tests is routine for medical care and would not require consent outside the scope of research. When subject arrives at CRC for the screening visit, the study team will begin with the consenting process as described above. We are only requesting the waiver of written consent for fasting to occur during the consenting visit. Written consent would be obtained prior to any study related procedures.

Recruitment Methods and Consenting Process (Arm 2)

- a. Potential mTBI subjects may be patients of the investigators.
- b. mTBI subjects will be recruited through ads and flyers around the community as well as in [name] Medicine Endocrinology clinic. The study will also be listed on the UTMB

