1. If paired household control subject withdraws consent, mTBI subject will be terminated from the study.
2. If subject reports they have missed more than 7 consecutive days of study medication administration, they will be terminated.

Household Control Subjects:

1. If paired mTBI subject withdraws consent or is terminated, household control subject will be terminated from the study.

Subjects enrolled in Arm 2 & 3:

mTBI/PASC Subjects:

1. If subject reports they have missed more than 7 consecutive days of study medication administration, they will be terminated.

Procedures and Time Frames for Communicating Outcomes:

Monitoring Reports will be prepared and forwarded to the IRB on an annual basis.

Precautions for Maintaining Data Integrity:

Careful monitoring of the recruitment, enrollment, retention, adverse events, and study procedures will help to protect the safety of study subjects, the quality of data, and the integrity of the study. As part of the safety plan for this study, the PI will review individual study subject records to ensure that appropriate mechanisms to protect the safety of study participants are being followed, that protocol requirements are being adhered to, and that data is accurate, complete, and secure. Subject records include consent forms, case report forms, flow of data forms, laboratory specimen records, inclusion/exclusion forms, cumulative toxicities and/or adverse event logs, and medical charts.

Records Retention

The investigator shall retain the records for 15 years.

Inclusion of Women and Minorities

Women and men will be included, as GENOTROPIN is approved for both.

Minorities will be included in the proportion found in the general population (see Targeted Enrollment Table)

Targeted/Planned Enrollment Table

Study Title: Brain and Gut Plasticity in mild TBI or post-acute COVID Syndrome Following Growth Hormone Therapy

Total Planned Enrollment: Up to 125 subjects. We would like to complete n=50 TBI subjects (enrolled in arm 1 and arm 2), n=50 control subjects (enrolled in arm 1 and arm 2) and n=25 PASC subjects (arm 3).

Targeted/ Planned Enrollment: Number of Subjects			
Ethnic Category	Sex/Gender		
	Females	Males	Total
Hispanic or Latino	13	12	25
Not Hispanic or Latino	50	50	100
Ethnic Category: Total of All Subjects *	63	62	125
Racial Categories			
American Indian/Alaska Native	0	0	0
Asian	0	0	0
Native Hawaiian or Other Pacific Islander	0	0	0
Black or African American	13	12	25
White	50	50	100

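### Arm 1 pair-termination rules diverge when a household control is terminated without withdrawing consent, and they end follow-up of a treated mTBI subject for aims that do not need that partner

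*Combined protocol and SAP*

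**What the plan says.** Two places govern what happens to one member of an Arm 1 pair when the other leaves.

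- Recruitment Methods and Consenting Process (Arm 1), item d, is symmetric: "If either one of the pair withdraws consent or is terminated, the other will be terminated by the study team".
- Stopping Rules, Arm 1, is not. For the mTBI subject: "If paired household control subject withdraws consent, mTBI subject will be terminated from the study". For the household control: "If paired mTBI subject withdraws consent or is terminated, household control subject will be terminated from the study".

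A control can become ineligible without withdrawing. Item 7 of the household control exclusion criteria reads "Pregnancy or become pregnant during the trial".

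On the aims, Specific Aim 3 is set out as "mTBI/PASC Baseline (month 0) vs. mTBI/PASC Month 6", Aims 4a to 4c are month 0 and month 6 measures, and the therapeutic rationale adds: "Each participant's baseline will serve as an individual control". Under Statistical Considerations, Aim 1b includes pre and post comparisons, and of the added mTBI subjects the plan says: "We expect to enroll subjects without the need for a HHC to address these differences". Those subjects form Arm 2, where the only listed stopping rule concerns missed study medication.

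On expected losses in Arm 1, section A (Risks to Human Subjects) says: "We also expect approximately 4 sets (8 total) of subjects to drop out during the course of the study". It plans screening and enrolment so that 25 pairs complete.

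**The concern.** There are two problems.

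First, the same event can be handled in two ways. If a control is terminated but has not withdrawn consent, staff who follow the consent section remove the mTBI partner, while staff who follow the Stopping Rules find no listed reason to do so. Whether a treated subject stays in the study should not depend on which page is consulted.

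Second, the documents do not separate the end of a pair from the end of data collection. A treated mTBI subject who is willing to go on loses the remaining stool samples and the month-6 visit because of another person's decision. These are the measurements that the pre/post aims need. fMRI is done in Arm 1 only, so Arm 2 cannot make up a lost month-6 scan. The pre/post set is then selected partly by partners' behaviour, and the plan does not say how terminated subjects are analysed.

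**Working it through.** **Step 1. Compare the two rules case by case.**

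| Event | Consent section, item d | Stopping Rules |
|---|---|---|
| mTBI subject withdraws | control terminated | control terminated |
| mTBI subject is terminated | control terminated | control terminated |
| Control withdraws consent | mTBI subject terminated | mTBI subject terminated |
| Control is terminated, consent not withdrawn | mTBI subject terminated | not listed |

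The texts agree in three cases. In the fourth, the Stopping Rules are silent.

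**Step 2. Does any stated analysis need intact pairs?** Under Statistical Considerations, power comes from a two-group t-test, and the outcome model is a standard repeated-measures ANOVA with no household or pair term named. Aim 1a pools Arm 1 and Arm 2 mTBI subjects (Enrollment section). Fatigue, cognition, mood, body composition and energy expenditure are not measured in household controls. So none of the stated analyses uses the pairing.

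**Step 3. Reproduce the plan's own figures.**

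- Arm 1 screening and enrolment: 50 completers + 8 dropouts + 20 screen failures = 78, as stated.
- Power for *Alistipes onderdonkii*, effect size 1.184, two-sided 0.05, noncentral t: 70.7%, 87.9%, 95.4% and 98.4% at 10, 15, 20 and 25 per group. All match the plan's table.

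**Step 4. How many treated subjects can the link cost?** Pairs enrolled after screening: 25 + 4 = 29. Pair loss: 4/29 = 13.8%. The plan does not say which member starts the loss.

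- Bounds: 0 if all four start with the mTBI subject, 4 if all four start with the control.
- Assuming equal and independent dropout at rate q per person, 1 − (1 − q)² = 4/29, so q = 1 − √(25/29) = 7.2%. Without the link, 29 × (1 − 0.0715) = 26.9 mTBI subjects would complete instead of 25, a cost of about 1.9.

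**Step 5. What does that do to precision?** The upper bound with replacement compares 25 mTBI subjects against 25 controls (link kept) with 29 against 25 (link dropped for the mTBI subject, all four losses started by controls). Effect sizes are back-solved from the plan's 10-per-group column.

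| Organism | 25/25 | 29/25 | Change |
|---|---|---|---|
| *A. onderdonkii* | 98.4% | 98.9% | 0.5 points |
| *Odoribacter* (lowest of the eight) | 91.2% | 93.0% | 1.8 points |

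For the two organisms that the plan lists at 66.4% and 61.2%, the change is about 3 points (to 69.7% and 64.3%).

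If lost pairs were not replaced, the comparison is 21/21 with the link against 25/21 without it: 96.3% and 97.5% for *A. onderdonkii*, 85.6% and 88.4% for *Odoribacter*.

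These are two-group figures and bear on the month-6 comparison only, because the baseline sample precedes any termination on study. The plan gives no power for the within-patient aims. For the Aim 3 correlation, with 80% power and a two-sided 0.05 test by Fisher's z, the detectable r is tanh[(1.960 + 0.842)/√(n − 3)]. It is 0.535 at n = 25 and 0.500 at n = 29 in Arm 1 alone. With both mTBI arms it is 0.387 at n = 50 and 0.373 at n = 54.

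**The case against.** The strongest reply is that Arm 1 is openly a household-pair design. Living with an eligible paired control is an inclusion criterion, candidates are told before consent that a partner is required, an extension after a further TBI applies to both members, and recruitment allows for four lost pairs. On that view, ending both members keeps the design intact and the cost has been budgeted. The design point stands. The documents still give no analytic reason for linked termination, and they specify no analysis that would use intact pairs.

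Several stronger readings are tempting, and the documents do not support them.

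- A reader might infer that the two rules give opposite instructions. They do not: the Stopping Rules omit a trigger and do not say that the mTBI subject stays.
- A reader might infer that data already collected are thrown away. No text says so. The headline Aim 1b contrast uses baseline samples, so only its pre/post part is exposed.
- A reader might infer that Aim 3 uses no control data. It does: Specific Aim 3 says that healthy controls supply control data, and the Enrollment section assigns controls from both arms to Aims 1 and 3. What holds is narrower: the within-patient contrast does not need that subject's own partner.
- A reader might infer that the target sample size falls. Section A plans to replace the expected losses so that 25 pairs complete. One caution is that the stated total enrolment of up to 125 equals the completer targets (50 + 50 + 25), so replacement rests on the Arm 1 text.

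A further objection is that a month-6 result describes six months of rhGH only if treatment went on. That is correct. It is a reason to record treatment exposure, and it does not argue for leaving the outcome uncollected.

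**Conclusion.** The point holds in limited form. The consent section and the Stopping Rules diverge in one of four cases and must be reconciled. The linked rule also creates avoidable, partner-driven missing data after termination in the within-patient contrasts of Aims 3 and 4 and in the pre/post part of Aim 1b.

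The size is modest: 0 to 4 of about 29 treated Arm 1 subjects, and about 2 under equal, independent dropout. The split between members is an assumption, because the plan gives only the number of pairs. The one-of-four divergence is a subset of these losses and cannot be sized separately. With replacement, power for the eight organisms moves by about 2 points or less. The case for change therefore rests on consistent handling and on not selecting the pre/post set by partners' decisions. It does not rest on a shortfall in planned power.

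**What to change.** 1. Reconcile item d of the Arm 1 consent section with the Arm 1 Stopping Rules, so that a control who is terminated without withdrawing consent leads to one stated outcome for the mTBI subject.
2. State that, when only the partner leaves and the mTBI subject still consents, the remaining stool samples and the month-6 outcomes are collected, and that all of that subject's data enter the analyses.
3. Flag such subjects as unpaired in the dataset, and record their treatment exposure so that the month-6 result can be interpreted.

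Whether study treatment continues after the partner leaves is for the investigator and sponsor to settle; nothing here depends on one answer.

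The cost is a short amendment, a few unpaired Arm 1 subjects, and one extra variable in the analysis.
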